Objectives	
 ● Main Objective: The primary endpoint is the estimate of HbA1c based on the mean of continuous glucose measurements obtained over the past 10 weeks for each pump use. 
The patient's glucose level (averaged over 10 weeks in each arm) will be calculated from measurements automatically recorded by a Continuous Glucose Measurement sensor that the patient already uses: the FreeStyle Libre (Abbott).
 
 ● Secondary Objectives: 
 ○ HbA1c values measured at the medical and biological laboratory at the beginning and end of the study ○ Glucose measurements (minimum, maximum, mean/median, standard deviation, out-of-range value, time in range[Time in Range] , variability) ○ Glycemic events (hypo- and hyperglycemia - as defined by the ADA, coma, other complications) ○ Skin and general tolerance ○ Technical incidents with the device

	
 ○ Overall patient satisfaction, out of the total study population, in each arm and the comparison between the two arms ○ Insulin treatment compliance
Study population	Type 1 or 2 diabetic patients already equipped with an Omnipod® insulin patch pump (Insulet) and a FreeStyleLibre® blood glucose sensor (Abbott).
Number of patients	75 diabetic patients (type 1 & 2) recruited in 3 months.
Duration of follow-up per patient	3 months from randomization. Follow-up visits at 4 weeks and 12 weeks. Patients randomized to the control arm (Omnipod) will be allowed to use an A7+Touchcare® pump for 1 full month after the 3-month visit if they wish, to facilitate recruitment by the centers and to allow for a satisfaction measure for both pumps.
Number of centers	8 centers in France (CHU and CHG).

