- Description of local skin tolerance at the pump site and at the FreeStyle Libre blood glucose sensor site).
- Description of any local or systemic safety issues reported during the study, including the additional one-month phase at the end of the study for patients in the "Omnipod" arm
- Description in the total population, in each group and comparison between groups of the number of patients who had at least one tolerance problem.

❖ **Incidents with devices**

- Description of any type of incident involving the operation of the medical devices used, particularly for pumps: pulling out, control problems, transmission difficulties, obstructions, leaks, etc.
- Description in each group, in the overall population and comparison between groups

❖ Patient satisfaction

- Description of the responses to the self-questionnaire assessing satisfaction with the use of the device (pump+PDM), in each group and in the total population
- Comparison of responses between groups
- Description of responses to the final question regarding patient preference between the Medtrum device and the Omnipod device: in each group and in the total population

❖ Insulin treatment

- Description of insulin doses delivered
- Description of any additional insulin injections with a pen during the study
- Description in the total population, in each group and comparison between groups

11.2.5 Tolerance analyses:

The analyses will be performed on the tolerance population.

Prior to any analysis all DM-related incidents and DM-related tolerance will be coded by the MedDRA regulatory medical dictionary (version 20.0 or later).

A summary table (number and percentage of patients with an AE and number of events) by organ system class (OSG) and preferred term (PT) will be presented for the following categories of events by dissociating DM-related incidents and tolerance:

- According to the link (device AND procedure),
- Depending on the link (device OR procedure),
- Depending on the severity,
- Depending on the actions taken (de-pairing).

A listing of individual data will be provided describing all the information collected via the eCRF concerning the IS (including duration, resolution, severity criteria, linkage, severity etc.)

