4 METHODOLOGY

4.1 GENERAL SCHEME OF THE STUDY

This is a longitudinal, randomized, comparative interventional study of type 1 or 2 diabetic patients requiring insulin treatment delivered by a patch pump. The study is multicenter in France, prospective, randomized in two parallel groups 1:1, open-label, with a non-inferiority methodology versus a comparator device (Omnipod® pump marketed by the company Insulet and which is already reimbursed in France since 23/02/2016).

It was planned that 75 type 1 or 2 diabetic patients would be included in the study by 8 hospital centers specialized in diabetes.

In order to facilitate the recruitment of patients already using an Omnipod® pump to be randomized into the Omnipod group (thus without changing their pump), it was proposed that these patients could use a Medtrum pump at the end of the study for 1 month. Thus, all patients in the study had the opportunity to use the new A7+ TouchCare® pump.

The expected duration of the study was: 1 month of set-up, 3 months of patient recruitment, 12 weeks of follow-up per patient, 1 additional month for patients in the Omnipod group to test the Medtrum pump, 3 months of data management, i.e. approximately 11 months of study.

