4.4.2 Secondary endpoints

The secondary endpoints were:

- HbA1c:
 - Value measured in the laboratory from a blood sample taken before the D0 visit and just before the 3-month visit
- Glucose Level Measurements
 - Average of glucose measurements over each time period and over the entire study duration
 - Minimum and maximum values
 - Time in range expressed as a %.

These values were automatically calculated by the FreeStyle Libre software and will be reported by the investigator.

- Glycemic events
 - Number of symptomatic and non-symptomatic hypoglycemic events during the evaluation period, broken down by severity level
 - Number of symptomatic and non-symptomatic hyperglycemia events over the evaluation period, broken down by severity level

This information was derived from the Free Freestyle data and the data entered by the patient in the MDP.

The definition of hypoglycemia and hyperglycemia is the ADA consensus definition:

Table 1—Summary of consensus definitions			
Outcome	Definition		
Hypoglycemia	Level 1: glucose <70 mg/dL (3.9 mmol/L) and glucose \geq 54 mg/dL (3.0 mmol/L) Level 2: glucose <54 mg/dL (3.0 mmol/L) Level 3: a severe event characterized by altered mental and/or physical status requiring assistance		
Hyperglycemia	Level 1—elevated glucose: glucose $>$ 180 mg/dL (10 mmol/L) and glucose \leq 250 mg/dL (13.9 mmol/L) Level 2—very elevated glucose: glucose $>$ 250 mg/dL (13.9 mmol/L)		
Time in range	Percentage of readings in the range of 70–180 mg/dL (3.9–10.0 mmol/L) per unit of time		

- Device tolerance
 - Local skin tolerance at the pump site (adhesive hold) and at the FreeStyle Libre blood glucose sensor site (adhesive hold)
 - Any local or systemic safety issues were to be reported during the study, including the additional one-month phase at the end of the study for patients in the Omnipod group
- Incidents with devices
 - Any type of incident involving the operation of the medical devices used, especially for pumps: pulling out, control problems, transmission difficulties, occlusion, leakage, etc.
- Patient satisfaction
 - Self-questionnaire evaluating satisfaction with the use of the device (pump + PDM)

- Final question regarding patient preference between the Medtrum device and the Insulet device
- Insulin treatment
 - The insulin treatment used should be documented

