4.4.3 Calculated/derived criteria

			2 = "More than 10 years
Number of years and months of treatment per pump	PUMP_D = Number of years * 12 + number of months	Time since starting pump therapy (in months)	Digital
Weight (kg) and height (cm)	BMI_D = (weight/height ²)*10000	Body Mass Index (BMI)	Digital
IMC_D	IMC4CL_D = -0 if BMI_D<18.5 -1 if BMI_D = [18,5 ; 25[-2 if BMI_D = [25; 30[. -3 if BMI_D >= 30	BMI (in classes)	0 = "Less than 18.5 1 = " [18,5 ; 25[" 2 = " [25 ; 30[" 3 = "Greater than 30
Tolerance variables	AL_PBTOL_D = -1 if the patient reported during the follow-up an irritation/itching problem or a redness problem or another adverse event -0 otherwise	Patient with at least one tolerance problem	0 = "No 1 = "Yes
HbA1c value measured in the laboratory at D0 and 3M	EVOL_HBA1C_D = HbA1c at M3 - HbA1c at D0	Evolution of HbA1c between D0 and 3M	Digital
Estimated HbA1c (FSL) (%)	EVOL_eHbA1c = HbA1c estimate at V2 - HbA1c estimate at D0 (will also be calculated for V3 and V4)	Evolution of HbA1c estimation between D0 and V2,V3,V4	Digital
Average blood glucose at different follow-up times	EVOL_GLYC_V2 = Average blood glucose at V2 - Average blood glucose at D0 (will also be calculated for V3 and V4)	Evolution of the average blood glucose level between D0 and V2, V3, V4	Digital
Average daily basal dose at different follow-up times	EVOL_BASAL_V2 = Average daily basal dose at V2 - Average daily basal dose at D0 (will also be calculated for V3 and V4)	Evolution of the average daily basal dose between D0 and V2, V3, V4	Digital
Average daily bolus dose at different follow-up times	EVOL_BOLUS_V2 = Average daily bolus dose at V2 - Average daily bolus dose at D0 (will also be calculated for V3 and V4)	Evolution of the average daily bolus dose between D0 and V2, V3, V4	Digital

Number of Boluses/day at different follow-up times	EVOL_NB_BOLUS_V2 = Number of Boluses/day at V2 - Number of Boluses/day at D0 (will also be calculated for V3 and V4)	Evolution of the number of Bolus/day between D0 and V2, V3,V4	Digital
Time of wearing the FSL	PORT_70sup = -1 wear time greater than 70%. -0 otherwise	FSL wear time greater than 70%.	0 = "No 1 = "Yes

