7.5 ANALYSIS OF TOLERANCE DURING THE STUDY

Analyses will be performed overall and by pump group on the **tolerance population**. Prior to any analysis, all DM-related incidents and DM-related tolerance will be coded by the MedDRA regulatory medical dictionary (version 20.0 or later).

The number of patients who had at least one tolerance problem will be described. The following criteria will be described for each period and by pump group:

- Irritation/itching (yes; no)
 - If yes, maximum intensity (low; moderate; intense)
- Redness (yes; no)
 - If yes, maximum intensity (low; moderate; intense)
- Other adverse events (yes; no)
 - All other events related to tolerance will be given in a listing.

A summary table (number and percentage of patients with AEs and number of events) by organ system class (OSG) and preferred term (PT) will be presented for the following categories of events by dissociating incidents and tolerance related to the medical device:

- According to the link (device AND procedure)
- According to the link (device OR procedure)
- Depending on the severity
- Depending on the actions taken (de-boosting)

A listing of individual data will be provided describing all the information collected via the eCRF concerning the AE (including duration, resolution, severity criteria, linkage, severity etc.)

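### The SAP sets no V3 cut-off and no pump-worn rule for the tolerance count AL_PBTOL_D and the SOC/PT adverse-event summary, so Medtrum-wear events in the extra month can land in the Omnipod column

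*SAP*

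**What the plan says.** - **Definition.** SAP 4.4.3 derives one yes/no value per patient, AL_PBTOL_D. It is 1 "if the patient reported during the follow-up an irritation/itching problem or a redness problem or another adverse event" and 0 otherwise. No visit limit and no pump-worn condition is attached.
- **Collection window.** SAP 4.4.2 asks for local and systemic safety issues to be reported, "including the additional one-month phase at the end of the study for patients in the Omnipod group". Protocol 7.6 reserves Visit 4 for patients randomized to Omnipod, after a month on the Medtrum pump, and collects tolerance data and adverse events there.
- **Protocol analysis.** Under device tolerance, Protocol 11.2.4 describes the safety issues reported, "including the additional one-month phase at the end of the study for patients in the" Omnipod arm. The next bullet calls for a "comparison between groups of the number of patients who had at least one tolerance problem".
- **SAP analysis.** SAP 7.5 works overall and by pump group on the tolerance population. "The number of patients who had at least one tolerance problem will be described", with no period attached. The SOC/PT summary is broken down by link, severity and action taken, again with no period. Irritation/itching, redness and other adverse events, by contrast, are described for each period and by pump group.

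**The concern.** In the extra month only one arm is under observation, and its patients are wearing the other arm's pump. A patient-level count that runs through V4 and is tabulated by randomized arm therefore credits Medtrum-wear events to Omnipod. It also gives that arm a longer time in which to have at least one problem. Both effects come from the same month and push the same way, towards the sponsor's device.

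The comparison matters because the known problem with such patches is local skin reaction to the adhesive (Protocol 3.1.4). Every participant already uses Omnipod at entry, so new reactions after a switch to Medtrum are plausible. A single figure for patients with at least one problem, and a SOC/PT table by arm, are the tolerance results most likely to be quoted.

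A smaller point concerns the same variable. Because AL_PBTOL_D is 0 in every other case, a pump user with no follow-up tolerance assessment is coded as problem-free. SAP 5.2 reports missing values and leaves them out of percentage denominators, but this variable as derived can never be missing.

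**Working it through.** The documents give no rate, sample size or power for tolerance, so there is no stated figure to reproduce. The check has two parts.

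**1. Does the text place V3–V4 events in the Omnipod column?**

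- *For a 12-week window.* The protocol synopsis gives the duration of follow-up as "3 months from randomization. Follow-up visits at 4 weeks and 12 weeks". SAP 4.1 lists "12 weeks of follow-up per patient, 1 additional month for patients in the Omnipod group to test the Medtrum pump" as separate items.
- *For a window through V4.* The SAP table that defines AL_PBTOL_D treats V4 as one of the follow-up times for glucose and insulin dose; one label reads "Evolution of the average blood glucose level between D0 and V2, V3, V4". SAP 4.4.2 places the extra month within the study for safety reporting.
- *Which column.* Protocol 7.3 uses the term pump group for the randomized allocation. Neither document gives the tolerance population an as-worn rule. AL_PBTOL_D is one value per patient, so it cannot be divided between two pumps.
- *Which events.* Protocol 13.2.1 keeps adverse events unrelated to the device or its procedure out of the eCRF. Pump-related events recorded in V3–V4 would therefore mainly concern Medtrum.

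A window through V4, tabulated by randomized arm, is the most natural reading, but it is not a stated rule.

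**2. How large would the effect be?**

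From the documents alone: 12 + 4 = 16 weeks of observation for Omnipod against 12 for Medtrum, and 16/12 = 1.33, or up to 33% more.

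The rest is illustration. Let p be the assumed risk of a tolerance problem per 4 weeks (pM on Medtrum, pO on Omnipod) and u the assumed share of Omnipod patients who take the extra month. Risk is taken as constant and independent between 4-week blocks.

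- With a V3 cut, each arm's proportion is 1 − (1 − p)³.
- Without it, the Omnipod proportion is 1 − (1 − pO)³(1 − u·pM).
- With equal pumps, the spurious difference is u·p·(1 − p)³.

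| p (both pumps) | Each arm at V3 | Omnipod uncut, u = 0.5 | Omnipod uncut, u = 1 | Spurious difference (points) |
|---|---|---|---|---|
| 5% | 14.3% | 16.4% | 18.5% | 2.1 to 4.3 |
| 10% | 27.1% | 30.7% | 34.4% | 3.6 to 7.3 |
| 15% | 38.6% | 43.2% | 47.8% | 4.6 to 9.2 |
| 20% | 48.8% | 53.9% | 59.0% | 5.1 to 10.2 |

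For example, at p = 0.20 and u = 1: 0.20 × 0.80³ = 0.20 × 0.512 = 0.102.

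Now suppose Medtrum is truly worse, with pM = 15% and pO = 5%:

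- Cut at V3: 1 − 0.85³ = 38.6% against 1 − 0.95³ = 14.3%, a Medtrum excess of 24.3 points.
- Uncut, u = 1: Omnipod reads 1 − 0.95³ × 0.85 = 27.1%, and the excess shrinks to 11.5 points.
- Uncut, u = 0.5: Omnipod reads 1 − 0.95³ × 0.925 = 20.7%, and the excess is 17.9 points.

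SAP 5.1 reports 100 patients included. Assuming 50 per arm from 1:1 allocation, a two-sided 5% comparison of proportions would have power of about 0.80 with the cut, 0.50 uncut at half uptake and 0.23 uncut at full uptake.

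**The case against.** The strongest reply is that follow-up already means 12 weeks. The synopsis and SAP 4.1 support it, and Protocol 7.6 places V4 after the end of the study. On that reading AL_PBTOL_D stops at V3. It is also true that the protocol's mention of the extra month and its between-group comparison are separate bullets, and that the comparison names no window. This stands to the extent that a reader should not infer a written rule charging Omnipod with Medtrum events. It does not settle the matter, because the SAP's own derivation table uses follow-up differently, and two programmers could reach different counts. Under SAP 10, tolerance outputs receive only the default check, not double programming.

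Second, much of the separation already exists. The three components of AL_PBTOL_D are described by period in SAP 7.5, device incidents are described by period in SAP 7.4.2, and the SAP's periods include V3–V4. A reader might infer that all the adverse-event tables run uncut through V4; the documents do not support that. The split is missing only from the patient count and the SOC/PT summary.

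Third, a reader might infer that a Medtrum safety signal would be hidden. That goes too far: the period rows, the individual listings, the recorded onset and causality (Protocol 13.2.1) and the independent committee (Protocol 13.4) do not depend on AL_PBTOL_D.

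Fourth, the SAP only describes the count; the between-group comparison stands in the protocol. The SOC/PT template in SAP 8 shows a Total column only, although the text of 7.5 says by pump group. This limits the weight of the point. Still, SAP 6 declares no change from the protocol's analyses, and unequal windows mislead in a descriptive table too.

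**Conclusion.** The point holds as an unspecified window and attribution rule for two outputs, AL_PBTOL_D and the SOC/PT summary by pump group. If followed on its most natural reading, the text biases the between-arm tolerance summary towards Medtrum.

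The 2–10 point range rests on equal pumps, a constant 5–20% risk per 4 weeks and 50–100% uptake, none of which the documents give. A reader might infer a larger figure by assuming that reactions cluster just after a switch. For instance, a 20% three-month risk with a 20% risk in the extra month and 90% uptake gives 0.80 × 0.90 × 0.20 = 14.4 points. But a constant 20% three-month risk is only 1 − 0.80^(1/3) = 7.2% per month, and nothing in the documents shows that clustering. Nor should misattribution and longer observation be added together as two biases, since they are largely one mechanism.

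This should be corrected before the tables are produced, but it is a secondary safety summary and not a must-fix. The coding of unassessed patients as problem-free is minor: the rule is the same in both arms, and the number affected is unknown.

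**What to change.** - In SAP 4.4.3, limit AL_PBTOL_D to events reported from D0 to V3. In SAP 7.5, apply the same limit to the SOC/PT summary and to the between-group comparison of patients with a tolerance problem that Protocol 11.2.4 requires.
- State that pump group means the randomized arm in these D0–V3 outputs.
- Tabulate V3–V4 events separately, labelled as Medtrum exposure in patients randomized to Omnipod, with the number who took up the extra month as denominator.
- Set AL_PBTOL_D to missing when a patient has no follow-up tolerance assessment, and report how many there are.
- Leave the irritation, redness, other-event and device-incident rows as they are.

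The cost is a few lines of SAP text and a filter on visit or onset date. No new data are needed.

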7.5 VISIT 3 (12 WEEKS): END OF STUDY VISIT

- Collect tolerance data and possible adverse events, and report them as required from the eCRF
- Verify the conditions of use of the devices by the patient
- Collect time-stamped records of glucose values (as well as HbA1c estimated from average glucose measurements) and glycemic events, hypoglycemia and hyperglycemia, insulin doses administered
- Collect technical incidents with the device (catheter occlusion, alarms, pump detachment, pain, allergy, etc.)
- Collect patient satisfaction and preference for either pump used (for Medtrum patients only)
- Recovering Medtrum materials
- Record all relevant data in the eCRF
- Offer the patient, if he is in the "Omnipod" group, to use a Medtrum pump for one month and make an appointment in one month for an end-of-study and material recovery visit

7.6 VISIT 4 (4 WEEKS AFTER THE END OF THE STUDY): AFTER 1 MONTH OF USE OF THE MEDTRUM PUMP (ONLY PATIENTS RANDOMIZED IN THE OMNIPOD GROUP)

- Collect tolerance data and possible adverse events, and report them as required from the eCRF
- Collect time-stamped records of glucose values (as well as HbA1c estimated from average glucose measurements) and glycemic events, hypoglycemia and hyperglycemia, insulin doses administered
- Collect technical incidents with the device (catheter occlusion, alarms, pump detachment, pain, allergy, etc.)
- Gather patient satisfaction and preference for either pump used
- Recovering Medtrum materials
- Record all relevant data in the eCRF

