3 OBJECTIVES OF THE STUDY

3.1 MAIN OBJECTIVE

The primary endpoint is the estimate of HbA1c at 3 months based on mean blood glucose measurements over the past 10 weeks for each pump use.

The patient's average blood glucose over the past 10 weeks was calculated in each arm from measurements automatically recorded by a continuous glucose sensor that the patient was already using: the FreeStyle Libre.

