4.4 EVALUATION CRITERIA

4.4.1 Primary endpoint

The primary endpoint is the estimation of HbA1c from the mean of glucose measurements over the last 10 weeks of follow-up.

Blood glucose levels were obtained from the measurements of the FreeStyle Libre continuous glucose sensor, extracted from the application provided by the manufacturer (already used in routine) and reported by the investigator in the eCRF. The investigator was asked to print the measurements from the software to facilitate monitoring of the reported data.

There will be no recalculation of the estimated HbA1c.

We have chosen to evaluate HbA1c obtained from a sensor measurement which is a good estimate of the average blood glucose level. The evolution of the classical HbA1c level is not informative on the time spent in hyper or hypoglycemia (whether or not the latter is symptomatic) because it does not reflect glycemic variability. In addition, the Nathan study highlights the reliability of estimating HbA1c over 14 days of continuous sensor measurements, as do the 2017 ADA Recommendations; more recently, the 2019 International Consensus on Time in Range recommendations reiterate the limitations of the HbA1c

criterion in the laboratory. The evolution of the monitoring of the effectiveness of insulin treatment is moving more and more towards average blood glucose and "Time in Range" (time spent in the target range/target values).

We propose to evaluate, as a secondary endpoint, the evolution of HbA1c measured in the laboratory from a blood sample at the beginning and at the end of the study, as well as the Time in Range which is automatically calculated from the data of the FreeStyle Libre reader.

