7.4 ANALYSIS OF THE EVALUATION CRITERIA

7.4.1 Primary endpoint analysis

The primary endpoint is the estimate of HbA1c at 3 months based on the mean of continuous glucose measurements obtained during the last 10 weeks of follow-up.

HbA1c estimation will be described by treatment group and then by type of diabetes.

The non-inferiority analysis of the primary efficacy endpoint will be performed with an ANCOVA, with the medical device as an explanatory variable and an adjustment on the estimate of HbA1c at Baseline, on the PP population.

If the upper bound of the IC95% of the Omnipod-Medtrum estimated difference in means (LSmeans) exceeds the non-inferiority bound set at 0.4, non-inferiority will not be demonstrated.

If non-inferiority is demonstrated, a superiority analysis will be conducted. If the upper bound of the IC95% of the estimated difference in mean is less than -0.3, superiority will be demonstrated.

The MIXED procedure (SAS® 9.4) will be used.

Code:

```
proc mixed data=XX order=data;
where PP = 1;
class DM;
model ESTIM_HBA1c = ESTIM_HBA1c_BASELINE DM;
lsmeans DM / diff=control cl;
run;
```

A sensitivity analysis will be performed on the ITTm population with imputation of missing data by the mean or median according to the distribution of the primary endpoint.

A subgroup analysis will be performed on the population of patients with an LSP wear rate >70% at M3.

Exploratory analysis:

Univariate analyses will be conducted on age in 2 classes (below or above the median), sex, type of diabetes, center, and duration of diabetes in 3 classes (<5 years; between 5 and 10 years; >10 years). If the p-value <0.05, the variable will be included in the full model. Then a top-down stepwise strategy will be conducted to select the variables for the final model.

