7.4.2 Secondary endpoint analyses

Analyses will be performed on the ITTm population.

Each variable will be described globally and by pump group.

The secondary endpoints are:

1. HbA1c

The evolution of HbA1c (measured in the laboratory) between D0 and 3M will be described, and a comparison between the groups will be made using a Student's t test or a Mann and Whitney test.

2. Glucose level measurement

The mean blood glucose level and its standard deviation (Blood Glucose Deviation SD) will be described over each period (between V1 and V2, then between V2 and v3, then between V3 and V4) and over the total duration of the study (mean, median, standard deviation, Q1-Q3, minimum and maximum). The coefficient of variation of glucose values will also be described.

The evolution of the average blood glucose level compared to baseline will be described at each visit.

FSL wear time (%) will be described.

The % of blood glucose values spent in target (time in range: [70; 180]), hypoglycemia (<70mg/dl), and hyperglycemia (>180 mg/dl) will be described over each time period in each pump group and in the total population.

For these criteria, comparisons between groups will be made using the Student or Mann-Whitney test.

3. Glycemic events

The number of hypoglycemic events will be described overall and in each period by severity level (according to ADA consensus definitions) overall and in each pump group.

Comparisons between groups will be made using Student or Mann-Whitney tests.

The % of time spent in hyperglycemia will be described overall and over each period and in each pump group. Comparisons between groups will be made using Student's t test or Mann and Whitney test.

4. Device tolerance

The analysis of this criterion is detailed in section 7.4 of this document.

5. Incidents with devices

The following criteria will be described for each period and by pump group (after reclassification):

- Pump occlusion (yes; no)
 - If yes, number of times
- Pump detachment (yes; no)
 - If yes, number of times
- Complete stop / breakage of the pump (yes; no)
 - If yes, number of times
- Other pump malfunction (yes; no)
 - All other possible malfunctions will be listed.

6. Patient satisfaction

The following criteria will be described for each period and by pump group:

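### SAP 4.4.3 derives every V4 change only against D0, so for Omnipod-arm volunteers the change after switching to Medtrum is not separated from the 12 study weeks before it

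*SAP*

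**What the plan says.** **Reference visit.** SAP 4.4.3 defines the change in mean glucose as "EVOL_GLYC_V2 = Average blood glucose at V2 - Average blood glucose at D0 (will also be calculated for V3 and V4" and the change in estimated HbA1c as "EVOL_eHbA1c = HbA1c estimate at V2 - HbA1c estimate at D0 (will also be calculated for V3 and V4". The rows for average daily basal dose, average daily bolus dose and number of boluses per day use the same D0 reference. SAP 7.4.2 repeats the baseline reference for mean glucose (item 2) and for the insulin variables (item 7). Neither document defines a V4 minus V3 change.

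**Who attends V4.** Protocol 7.6 limits V4 to patients randomised to Omnipod, after one month on Medtrum. Protocol 7.5 makes that month an offer, so V4 patients are volunteers from one arm. The synopsis gives satisfaction as the purpose of the visit.

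**Windows.** For mean glucose, SAP 7.4.2 sets inter-visit periods: "over each period (between V1 and V2, then between V2 and v3, then between V3 and V4". For eHbA1c, the only window in either document is 10 weeks, and it belongs to the 3-month primary endpoint: "the mean of continuous glucose measurements obtained during the last 10 weeks of follow-up" (SAP 7.4.1). Protocol 7.4 to 7.6 ask sites to "Collect time-stamped records of glucose values (as well as HbA1c estimated from average glucose measurements) and glycemic events", without naming a period for the eHbA1c value. SAP 4.4.1 adds: "There will be no recalculation of the estimated HbA1c".

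**The concern.** The natural question about the extension month is what happened after the volunteers left Omnipod. Their last Omnipod value is at V3. D0 is 12 weeks earlier, and those 12 weeks are spent in a trial, on an unchanged pump. Anything that moved glucose or insulin use in that time, such as trial participation or season, enters V4 minus D0 in full and would be read as part of the Medtrum month.

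No other planned analysis separates the two parts. The between-group tests in SAP 7.4.2 cannot be applied to V3–V4, which contains one randomised group. Protocol 11.2.4 foresees paired tests for within-group changes, but the SAP names none.

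The unstated eHbA1c window is a second, smaller gap. Sites transcribe the value from the sensor software, it is not recalculated, and under Protocol 9.1 neither the sponsor nor the CRO can open the applications. If sites chose different windows, this would be hard to see or repair centrally.

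**Working it through.** The plan states no figure on this point to reproduce, and its sample-size figures do not depend on it.

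**Inputs.** V2 is at day 28 and V3 at day 84 (Protocol 7.1). V4 is 4 weeks after V3, so day 112 (Protocol 7.6). One month is 28 days, or 30.44 days by the SAP 4.4.3 conversion. The primary-endpoint window is 70 days (SAP 7.4.1). The sensor reader stores at most 90 days (Protocol 3.4.1). Assumption: the Medtrum pump is started on the day of V3 (Omnipod arm) or V1 (Medtrum arm).

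**1. What V4 minus D0 contains.**

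V4 − D0 = (V3 − D0) + (V4 − V3)

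The first term is entirely on Omnipod; the second is the change after the switch. The documents give no size for the first term, so a range is assumed, with a true post-switch rise of 0.2 points:

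| Assumed V3 − D0 | V4 − V3 | Reported V4 − D0 |
|---|---|---|
| −0.2 | +0.2 | 0.0 |
| 0.0 | +0.2 | +0.2 |
| +0.2 | +0.2 | +0.4 |

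**2. Mean glucose under the periods in SAP 7.4.2.** V2–V3 covers days 28–84, all on Omnipod for these patients. V3–V4 covers days 84–112, all on Medtrum. The pre-switch share of V3–V4 is 0%, so a paired contrast of these two periods is clean of overlap. Those periods start at V1, so D0 mean glucose has no stated period, whereas V2–V3 does.

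**3. eHbA1c if a look-back of W days were used at V4.**

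Pre-switch share = 1 − min(days on new pump, W)/W

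A true change of 0.4 points, assumed immediate and constant in an unweighted mean, shows as 0.4 × min(days on new pump, W)/W.

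| W (days) | Pre-switch share, 28 / 30.44 days on pump | 0.4 shows as |
|---|---|---|
| 14 | 0% / 0% | 0.40 / 0.40 |
| 28 | 0% / 0% | 0.40 / 0.40 |
| 30 | 6.7% / 0% | 0.373 / 0.40 |
| 70 | 60% / 56.5% | 0.16 / 0.174 |
| 90 | 68.9% / 66.2% | 0.124 / 0.135 |

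Only the 70-day window appears in the documents, and not for V4. The 28-day figures also apply at V2, in the Medtrum arm only.

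**4. Changing the reference alone is not enough for eHbA1c.** With 70-day windows, V3 covers days 14–84 and V4 days 42–112. They share 84 − 42 = 42 days, and 42/70 = 60%.

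**5. Primary endpoint.** At V3 the window starts at 84 − 70 = day 14, after randomisation. Its pre-switch share is 0%.

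**The case against.** The strongest reply has four parts.

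- **Change from baseline is conventional.** For extension patients D0 and V3 are both on Omnipod, so V4 minus D0 is still an Omnipod-to-Medtrum change. That stands, and it is why V4 minus D0 need not be removed. It does not make the 12-week component disappear.
- **The period summaries already show V2–V3 beside V3–V4.** They do for most glucose variables and for doses. But V2–V3 describes the whole Omnipod arm and V3–V4 only the volunteers, so the two summaries may differ because the patients differ. They do not replace a paired contrast.
- **The window argument touches little.** A reader might infer that V2 and V4 results rest largely on glucose from before the switch. The documents do not say so. The 10-week window is tied to the 3-month endpoint, and SAP 3.1 words it as "based on mean blood glucose measurements over the past 10 weeks for each pump use", which points away from a window spanning two pumps. Mean glucose has its own periods, and doses come from the pump record. SAP 7.4.2 lists no analysis of the eHbA1c change at all. What remains is an unstated window for one derived variable; the 60% and 0.16 are conditional.
- **The extension matters little.** A reader might take it as the trial's only within-patient view of Omnipod followed by Medtrum. It is not: every participant enters on Omnipod and the Medtrum arm switches at randomisation. V4 is optional and mainly serves recruitment and satisfaction. This stands and limits the point to secondary results.

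**Conclusion.** The point holds for the reference visit. As derived, V4 minus D0 cannot be read as the change after switching, because it carries in full any change over 12 study weeks on Omnipod. The size of that component is not known from the documents; the ±0.2 points above is an assumption that shows the mechanism.

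For eHbA1c the supported finding is narrower: the window at D0, V2 and V4 is not stated. The dilution of 0.4 to about 0.16–0.17 arises only if the 10-week window is used, and assumes an immediate, constant shift.

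A V4 minus V3 change is still an uncontrolled before-and-after comparison in volunteers. It removes the change before V3, not any time effect during the extension month itself. The impact is confined to secondary, descriptive results. The primary endpoint, sample size and error rates are untouched.

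**What to change.** 1. In SAP 4.4.3 and 7.4.2, add a paired V4 minus V3 change for the five variables, in extension participants with both values, and make it the reported change after switching. Use the paired methods already named in Protocol 11.2.4 if a test is wanted. V4 minus D0 may stay as a supplementary description, labelled as including the 12 weeks on Omnipod.
2. For glucose, base this contrast on mean glucose over V2–V3 and V3–V4, and state in 4.4.3 that a value at V4 means the V3–V4 period.
3. State the eHbA1c window at D0, V2 and V4. At V2 and V4 limit it to the inter-visit period or, if that cannot be exported or sites have already extracted over another window, report period mean glucose instead.

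The cost is five derived variables, one summary table and one line of extraction instructions, all before database freeze. V3 values are already collected, so items 1 and 2 need no new data.
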